#### Figure 1-1 Study Design

The primary endpoint data for efficacy is collected at Week 48.

[figure not shown]
In case of any protocol amendment, this SAP may be amended accordingly.

#### 1.2 Study objectives and endpoints

#### Table 1-1 Objectives and related endpoints

-			
Objective(s)	Endpoint(s)		
Primary objective(s)	Endpoint(s) for primary objective(s)		
• To demonstrate the efficacy of tropifexor + licogliflozin as assessed by histologic improvement after 48 weeks of combination treatment compared to each monotherapy treatment in patients with NASH and stage 2 or 3 fibrosis.	Proportion of patients with resolution of NASH and no worsening of fibrosis OR improvement in fibrosis by at least one stage without worsening of NASH (no worsening of hepatocellular ballooning or lobular inflammation) at Week 48 compared with baseline. The criteria for resolution of NASH (absence of ballooning with no or minimal inflammation by histology) and other changes in histologic endpoints are further detailed in Section 5.3.11 .		
Secondary objective(s)	Endpoint(s) for secondary objective(s)		

 
Improvement in fibrosis by at least one stage with no worsening of NASH after 48 weeks of treatment
 
	• Key secondary endpoint: Proportion of patients who have at least one stage improvement in fibrosis without worsening of NASH (no worsening of hepatocellular ballooning or lobular inflammation) at Week 48 compared with baseline		

Objective(s)	Endpoint(s)

 
Resolution of NASH with no worsening of fibrosis after 48 weeks of treatment
 
	
 
Key secondary endpoint: Proportion of patients with resolution of NASH and no worsening of fibrosis at Week 48 compared with baseline
 

 
Improvement in fibrosis by at least one stage
 
	
 
Proportion of patients who have at least one stage improvement in fibrosis at Week 48 compared with baseline
 

 
Improvement in fibrosis by at least two stages with no worsening of NASH after 48 weeks of treatment
 
	
 
Proportion of patients who have at least two stage improvement in fibrosis without worsening of NASH (no worsening of hepatocellular ballooning or lobular inflammation) at Week 48 compared with baseline
 

 
Reduction in body weight from baseline after 48 weeks of treatment
 
	
 
Proportion of patients with 5% or more reduction in body weight at Week 48 compared to baseline
 

 
Change in liver fat content after 48 weeks of treatment
 
	
 
Change in liver fat content based on MRI - PDFF over time up to Week 48 compared with baseline
 


 
To determine the relationship of investigational treatment and markers of hepatic inflammation in NASH (AL and AST)
 
	

 
To determine the relationship of investigational treatment and GGT, a marker of cholestasis and oxidative stress
 
	
 
Change in GGT over time up to Week 48 compared with baseline
 

 
To evaluate the safety and tolerability of tropifexor (LJN452) in combination with licogliflozin (LIK066), compared to monotherapy of each compound from baseline
 
	

# 2 Statistical methods

# 2.1 Data analysis general information

This SAP guides the statistical analysis for the core CSR after all patients complete (including early withdrawal) the study. There is no planned interim analysis for statistical inference. DMC analyses are described in a separate SAP.

Novartis statisticians and programmers will perform this statistical analysis, primarily using SAS 9.4 or newer. Additional analysis software (e.g. R), in their newest versions available in the validated data analysis environment, may also be used.

Descriptive summaries will be presented by study treatment without a total column, unless requested in a specific section. Categorical variables will be summarized with count and percentages. If not otherwise specified, continuous variables will be summarized with n, arithmetic mean, standard deviation, minimum, maximum, median, first quartile and third quartile.

Confidence intervals (CI) in this SAP refers to 2-sided confidence intervals unless clarified differently. P-values will be reported only if a formal hypothesis test is performed.

Analyses performed at pre-specified analysis visits, including the primary efficacy endpoint at week 48, will be based on the analysis visit instead of original CRF visits. The derivation of analysis visits is detailed in Section 2.1.1. As an example, if the scheduled visit 5 (W4) of a patient is delayed and occurs on study day 48 instead of on Day 28, the data from that visit will be mapped to analysis visit 6 (W8).

Analysis by visit (or "over time") will present baseline and only post-baseline visits at which an assessment for the endpoint is scheduled according to protocol (Protocol Table 8-1). Summaries at post-baseline visit will include only patients with non-missing baseline and at least one non-missing post baseline results for the endpoint.

Data listings will be presented by study treatment and include, in addition to the columns explicitly requested in specific section, following columns: patient ID, age/gender/race, first/last dose date of study treatment and date (study day) of assessment/event/sampling. All listings will present data as collected without any imputation needed for other data analysis purpose.

#### 2.1.1 General definitions

**Study treatment** in this SAP refers to the investigational regimens, i.e. the combination of tropifexor (LJN452) 140  $\mu$ g and licogliflozin (LIK066) 30 mg, or each of them as monotherapies combined with matching placebo for the other. For simplicity hereafter, "LJN452" and "LIK066" in this SAP refer to the two specific dose strength of LJN452 140  $\mu$ g and LIK066 30 mg unless otherwise specified.

**Date of first study treatment ("first dose date" or "FDDT" )** is the date of first administration of study treatment during the study as recorded in eCRF (Dosage Administration Record summary page).

**Date of last study treatment ("last dose date" or "LDDT")** is the date of last administration of study treatment during the study as recorded in eCRF (Dosage Administration Record summary page).

Study day is number of days counted from the first dose date (Day 1).

For dates on or after FDDT, study day = date of interest - FDDT + 1.

For dates prior to FDDT, study day = date of interest – FDDT.

If first dose date is missing, the randomization date will instead be used for the calculation.

**Baseline** for analysis, in general, is the last assessment with valid data before the date and time of first administration of study treatment. If the date of assessment is the same as first dose date but time is not available for comparison, the assessment is assumed to be prior to the administration of study treatment. For ALT, AST, ALP, GGT and total bilirubin, however, the baseline is the average of values from two screening visits and the baseline visit collected before first administration of study treatment. If there is unscheduled visit with lab assessment after a planned screening visit, the value from this unscheduled visit will also be used in the calculation of baseline.

End of study (EoS) or last contact date of a patient is the date of his/her last office visit or other route of follow-up in the study.

**Treatment period** is the period from the Baseline visit (included) to the TD/EOT (W48) visit (included) as defined in protocol Table 8-1.

Follow-up period is the period from TD/EOT (W48) visit (not included) to EoS (included).

**Analysis visit** is the visit label derived based on study day of assessment and the analysis visit windows defined in Table 2-1. For laboratory and bioanalytical parameters specified for both Group 1 and Group 2 in Table 2-1, two sets of analysis visits will be derived and will be referred to as "**AV1**" and "**AV2**" respectively. The AV1 is derived according to Group 1 for by visit analysis on full analysis set (FAS). For AV2, assessments >14 days after the last dose date will be slotted into the analysis visit window for follow up visit for by-visit analysis of laboratory data on safety analysis set (SAF).

**Analysis visit windows** are non-overlapping periods each associated with a visit planned in protocol and all together cover the entire study period of a patient. If multiple measurements of same parameter for a patient fall in the same window, the value of this analysis visit is selected according to Table 2-2. If no assessment falls into a window, the value of that analysis visit will be set to missing unless imputation rule(s) are defined for the parameter. Repeat and unscheduled visits will be mapped to analysis visits in the same way as scheduled visits.

#### Table 2-1Analysis visit windows

Analysis Visit Windows

Novartis	For business use only	Page 14
SAP		CLJN452D12201C

Analysis Visit	Target Study Day	Group 1	Group 4	Group 5
Baseline	1	≤ 1*	≤ 1*	≤ 1*
Week 2	15	2-22		
Week 4	29	23-43		
Week 8	57	44-71		
Week 12	85	72-99	2-127	2-169
Week 16	113	100-127		
Week 20	141	128-155		
Week 24	169	156-197	128-253	
Week 32	225	198 – 253		
Week 40	281	254 – 309		
Week 48	337	310 – 351	254 - 351	170 - Eos
Wk 52/FU	365#	352 – EoS	352 - EoS	NA

\* The first dose date of the study is defined as Day 1. If first dose date is missing, the date of randomization will be used as day 1.

# The target study day for the FU visit of Group 2 will be LDDT+28

Group 1: vital signs and anthropometric measurements, liver function tests (ALT, AST, TBL, Albumin, ALP and GGT), lipids panel, coagulation panel, BUN, creatinine, eGFR

Group 4: Waist/Hip circumference, Group 5: MRI, liver biopsy

Table 2-2	Choose value among multiple assessments in the same analysis visit
wir	ıdow

willuow		
Timing of measurement	Type of data	Value selection rules
Baseline	All data excluding ALT,	Choose the latest non-missing measurement before the first administration of study treatment (FDDT).
	AST, ALP, GGT, TBL,	If a patient did not receive any dose of study treatment, the latest measurement on or before the randomization date is used.
		If the date of a measurement is the same as FDDT but time is not available for comparison, the measurement is assumed to be prior to the first administration of study treatment.
	ALT, AST, ALP, GGT, TBL,	The average of valid values from all visits before first administration of study treatment will be calculated as baseline.
Post-baseline	Continuous parameters	Choose the measurement closest to the target study day. If more than one measurements on the same date, choose the last (based on time, or visit label if time not available) measurement on that day.

Timing of measurement	Type of data	Value selection rules
		If two measurements are equally away before and after the target study day, use the mean.
	Categorical efficacy parameters	Choose the measurement closest to the target study day. If more than one measurements on the same date, choose the last (based on time, or visit label if time not available) measurement. If two measurements are equally away before and after the target study day, use the first measurement.
	Notable laboratory abnormalities; shift from baseline;	The most extreme measurement in the window will be used. Note that this means a patient can have a notably high and notably low measurement within a window.

Geographical regions are defined according to countries of study sites at which patients are randomized:

Table 2-3	Geographical regions
Region	Countries
Europe	Belgium, Bulgaria, Denmark, Estonia, France, Germany, Italy, Russia and CIS, Spain, United Kingdom
North America	a Canada, USA,
Latin America	Argentina, Brazil, Canada, Chile, Colombia, Mexico
Asia	China, India, Japan, Singapore, South Korea, Taiwan,

Australia, Egypt, Saudi Arabia, South Africa, Turkey

#### 2.2 Analysis sets

Other

The following analysis sets are defined for analysis purpose:

Screened analysis set (SCR) comprises of all patients who signed the informed consent. This analysis set includes also screen failures.

Randomized set (RAN) comprises of all patients who received a randomization number, regardless of whether patient received study medication. Mis-randomized (not qualified for randomization but randomized inadvertently) patients will be included in this analysis set.

Full Analysis Set (FAS) comprises of all patients to whom study treatment has been assigned by randomization. Patients who were mis-randomized (not qualified for randomization but randomized inadvertently) and did not receive investigational medication are excluded from the FAS. Efficacy analysis will be conducted on FAS. Following the intent-to-treat (ITT) principle, patients are analyzed according to the study treatment assigned during the randomization regardless of actual treatment received and according to the true stratum the patient belongs to in case a patient is assigned to wrong stratum during randomization.

Safety Analysis Set (SAF) includes all patients who received at least one dose of study treatment. Patients with the following unusual situations, if it occurs, will be excluded from SAF.

- Had no safety assessment after first dose of study treatment (e.g. lost to follow-up). Of note, the statement that a subject had no adverse events constitutes a safety assessment.
- Took only matching placebo tablet or capsules during the study. Of note, such situation will be identified only after study unblinding.

SAF will be used for analysis of Safety

in this SAP.

In the SAF, patients will be analyzed according to the study treatment received, where treatment received is defined as the randomized/assigned study treatment if the patient took at least one dose of that treatment or the first treatment received if the randomized/assigned study treatment was never received.

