6.1.3 Treatment arms/group

Participants (n = 380) will be assigned at Baseline visit to one of the following 4 treatment arms in a ratio of 1.75:1:1:1 in a blinded manner. Placebo capsules/tablets will be given in each treatment arm where necessary to maintain blinding.

Arm A: Combination therapy Arm - (N=140): tropifexor 140 μ g + licogliflozin 30 mg, once daily.

Arm B: Tropifexor monotherapy Arm - (N=80): tropifexor 140 μ g (+ placebo matching licogliflozin), once daily.

Arm C: Licogliflozin monotherapy Arm - (N=80): licogliflozin 30 mg (+ placebo matching tropifexor), once daily.

Arm D: Placebo Arm – (N=80): placebo matching tropifexor + placebo matching licogliflozin, once daily.

The 140 μ g dose of tropifexor and its matching placebo are each now available as a single hard gelatin capsule. Participants participating at the time of availability of the single tropifexor/placebo capsule, may continue on the 3-capsule tropifexor (100 μ g + 30 μ g + 10 μ g) or matching placebo regimen until the available 3- capsule supply is depleted. After the 3-capsule tropifexor or matching placebo supply is depleted, participants will take one 140 μ g tropifexor or matching placebo capsule daily. No change is made to licogliflozin dosing. Further details can be found below and in Section 6.7.2.

6.1.3.1 Dosing with 3 capsule $(10 + 30 + 100 \mu g)$ tropifexor supply

Until 3-capsule tropifexor ($100 \ \mu g + 30 \ \mu g + 10 \ \mu g$) and matching placebo is replaced by the 140 μg hard gelatin single capsule, in order to maintain the blind, placebo capsules matching tropifexor (LJN452) 10, 30 and 100 μg and placebo tablets matching licogliflozin (LIK066) 10 mg will be given to participants as indicated in Table 6-5, so that all participants will receive 3 capsules and 3 tablets per day. **One capsule from each of the 3 bottles**, and **3 tablets from the blister pack** should be taken close to the evening meal; either just prior to (within 5 minutes) consuming the evening meal, or no more than 30 minutes after consuming the evening meal and at about the same time each day.

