12.1 Analysis sets

Following analysis populations will be defined for the statistical analysis:

Screened analysis set (SCR) comprises of all participants who signed the informed consent.

Randomized Analysis set (RAN) comprises of all participants who received a randomization number, regardless of whether participants received study medication.

Full Analysis Set (FAS) comprises of all participants to whom study treatment has been assigned by randomization. Participants who were mis-randomized (not qualified for randomization but randomized inadvertently) and did not receive investigational medication, however, are excluded from the FAS. Efficacy analysis will be conducted on FAS. Following the intent-to-treat (ITT) principle, participants are analyzed according to the treatment they have been assigned during the randomization procedure regardless of actual treatment received and the true stratum the participant belongs to if a participant is assigned to wrong stratum during randomization.

Safety Analysis Set (SAF) includes all participants who received at least one dose of study treatment. Participants will be analyzed according to the study treatment received, where treatment received is defined as the randomized/assigned treatment if the participant took at least one dose of that treatment or the first treatment received if the randomized/assigned treatment was never received.

The number of participants in each analysis set will be presented by treatment group and overall for the screen set.

The number and percentage of participants in the randomized set who completed the study, who discontinued the study and the reason for discontinuation will be presented for each treatment group and all participants. The frequency (%) of participants with protocol deviations and criteria leading to their exclusion from each analysis set will be presented for randomized set.

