# 1.1 Study design

[figure not shown]
This is a randomized, double-blind, parallel-group, multiple-arm study to assess the efficacy, safety and tolerability of tropifexor and licogliflozin combination therapy compared to each monotherapy in patients with non-alcoholic steatohepatitis (NASH) and advanced fibrosis.

The study consists of 1) a screening period, 2) a treatment period starting from randomization on Day 1 and running to Week 48, and 3) a follow-up period of 4 weeks after the last dose of study treatment. The screening period starts from the time of the signing informed consent and continues for up to 8 weeks when all inclusion/exclusion criteria have been evaluated and all baseline assessments have been performed. The study duration from first dose of study medication is 52 weeks. The total duration of participation may be up to 60 weeks.

Approximately 210 patients with NASH and F2-F3 fibrosis will be randomized in a 1:1:1 ratio to one of the following treatments:

- Arm A: tropifexor + licogliflozin combination therapy,
- Arm B: tropifexor monotherapy,
- Arm C: licogliflozin monotherapy

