# 2.8 Safety analyses

All safety analyses will be on SAF and presented by study treatment actually received (Section 2.2).

If not clarified otherwise, safety summaries will include only data from the on-treatment period except that baseline data may also be summarized where appropriate (e.g. change from baseline summaries). The on-treatment period lasts from the date of first administration of study treatment to 30 days after the date of the last dose date.

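### The only SAP supplied predates the placebo arm; carried over unchanged, its safety-set rule would drop all 80 placebo participants and conflict with protocol 12.1

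*SAP*

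**What the plan says.** **Protocol (Amended Version 02).** Section 6.1.3 assigns 380 participants to four arms at 1.75:1:1:1. Arm D (N=80) receives "placebo matching tropifexor + placebo matching licogliflozin". Section 12.1 states: "Safety Analysis Set (SAF) includes all participants who received at least one dose of study treatment". It adds an as-treated rule but no exclusions. The Glossary counts control drugs as study treatment, so a dosed Arm D participant qualifies. Table 2-1 lists, as a secondary objective, the safety and tolerability of the combination and of each monotherapy against placebo. Section 12.5.2 bases all safety analyses on the safety set.

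**SAP.** The document history has one entry, 09-Dec-2019, before the first patient's first visit.

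- Section 1.1: "Approximately 210 patients with NASH and F2-F3 fibrosis will be randomized in a 1:1:1 ratio to one of the following treatments". The three arms are the combination, tropifexor and licogliflozin.
- Section 2.1.1 defines study treatment as the combination of the two drugs, "or each of them as monotherapies combined with matching placebo for the other".
- Section 2.2 opens in the same way as the protocol: "Safety Analysis Set (SAF) includes all patients who received at least one dose of study treatment". It then adds: "Patients with the following unusual situations, if it occurs, will be excluded from SAF". Two situations follow. One is having no safety assessment after the first dose. The other is a patient who "Took only matching placebo tablet or capsules during the study", which the SAP notes can be recognised only once the study is unblinded.
- Section 2.8: "All safety analyses will be on SAF and presented by study treatment actually received". Section 2.4 also places exposure and compliance on the SAF.

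**The concern.** Taking only matching placebo is an anomaly in the SAP's design, but in the current protocol it is the assigned regimen of a whole arm. Read against the four-arm design, the SAP bullet describes every compliant Arm D participant.

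At stake is the interpretability of the safety results. SAP 2.8.1.1 plans by-treatment counts for pruritus, diarrhea, hypoglycemia and pancreatitis, and Kaplan-Meier curves for the first three. Protocol 1.1.3 reports pruritus on placebo in the earlier tropifexor study. Protocol 1.1.4 reports diarrhea in similar numbers on placebo and on licogliflozin 30 mg. Rates on the active arms cannot be judged without the background rate.

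There is also a timing problem. Because the SAP says the situation is identifiable only after unblinding, the effect of the bullet would show itself only then, and any repair would be a change to an analysis set made with treatment codes known.

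**Working it through.** The question is one of set membership, so the arithmetic is short.

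**Step 1. Reproduce the protocol's arm sizes** (N = 380, ratio 1.75:1:1:1, Protocol 6.1.3).
- Sum of ratio parts: 1.75 + 1 + 1 + 1 = 4.75.
- Placebo and each monotherapy: 380 × 1/4.75 = 80.
- Combination: 380 × 1.75/4.75 = 140.
- These match the stated 140, 80, 80 and 80.

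**Step 2. Apply each SAF rule to each design.**

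| Design | SAF rule | Placebo arm planned | Placebo arm kept | Maximum SAF |
|---|---|---|---|---|
| SAP 1.1 (210, 1:1:1) | SAP 2.2 | 0 | no such arm | 210 |
| Protocol v02 (380) | Protocol 12.1 | 80 | up to 80 | 380 |
| Protocol v02 (380) | SAP 2.2, unchanged | 80 | 0 | 300 |

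In the first row the arms are 210/3 = 70 each and all contain an active drug, so the bullet can remove only stray individuals. In the third row the loss is 380 − 300 = 80, and 80/380 = 21.1%.

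**Step 3. Check whether deleting the bullet is enough.** It is not. The opening clause of SAP 2.2 requires a dose of study treatment, and SAP 2.1.1 gives that term only three regimens, each with at least one active drug. On a literal reading an Arm D participant fails the opening clause before the exclusion is reached.

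**Step 4. Check the SAP against itself.** Table 5-6 in SAP 5.5 lists the scenarios that exclude subjects from analysis sets. For the SAF alone it gives only the case of no drug taken after randomization. Neither the placebo-only exclusion nor the no-safety-assessment exclusion appears there, and neither is in protocol 12.1. Removing both would bring SAP 2.2 into line with both places.

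**The case against.** The strongest reply is that the rule was sound for the design it was written for. In a three-arm double-dummy trial, a patient who took only the dummy product never received an active drug, and the SAP calls this an unusual situation. The placebo arm came with protocol Amendment 01, dated 18-Sep-2020. The SAP says it may be amended after a protocol amendment. Protocol v02 refers model, imputation and sensitivity details to the SAP (Sections 12.4.2, 12.4.4 and 12.4.5), which presupposes one that fits four arms. The same SAP also still has 210 patients, a composite primary endpoint and a one-sided 0.05 level, so this bullet is one symptom of a document that was not updated.

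All of that stands. A reader might infer that the trial's current plan discards its placebo arm from the safety analyses, or that the rule was an error when written. The documents support neither. The SAP has no placebo arm to discard, and the current protocol's definition keeps all dosed placebo participants.

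What the reply does not remove is the conflict itself. A statement that the SAP may be amended is not a commitment, and no amended SAP is among the documents. An update that revises the arms, sample size, alpha and endpoints could leave this line in place, because it reads as standard text. It therefore needs to be named separately.

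**Conclusion.** Wrong as written: the SAP's SAF rule conflicts with the current protocol. Carried over unchanged, it would remove all 80 planned placebo participants (21% of 380), reduce the SAF to at most 300, and leave the stated safety comparison with placebo without a control group.

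The size rests on three assumptions: the planned 80 are all randomized and dosed; none takes an active product by error, since such a person would escape the exclusion; and the SAP text is applied literally to the four-arm design. Under protocol 12.1 the loss is zero. Whether an amended SAP exists cannot be told from the documents.

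The exclusion of participants with no safety assessment after dosing is a separate and minor mismatch. The SAP narrows it by counting a report of no adverse events as an assessment, and the documents give no basis for estimating how many people it would affect.

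**What to change.** When the SAP is updated to the four-arm design, and before unblinding:

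1. Delete the placebo-only exclusion from SAP 2.2 and adopt the protocol 12.1 SAF definition, including its as-treated rule. Limiting the bullet to participants randomized to an active arm would protect Arm D, but would still depart from protocol 12.1; deletion is cleaner.
2. Add the double-placebo regimen to the definition of study treatment in SAP 2.1.1.
3. Add placebo as a group, and comparisons with it, to the by-treatment safety summaries in SAP 2.8 and to the exposure and compliance summaries in SAP 2.4.1.
4. As a minor alignment, remove the exclusion for no safety assessment after the first dose.

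Items 1, 2 and 4 are wording changes. They are not sufficient alone, because the SAP's arms, objectives and comparisons contain no placebo group. They belong in the full four-arm revision that the SAP needs in any case. Nothing here alters data collection or trial conduct.
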